9.2 Design

The focus of this study is to determine the difference in mental health parameters following the participation of cancer patients in a creative writing workshop. Participants will be randomized within strata formed by cancer type in order to assure that these potentially important confounding variables are balanced across groups. Patients will be enrolled on a rolling basis over a four to five-month period, allowing patients in intervention arm to participate in 2-3 months workshops (workshops would be held once every 2 weeks). Patients in control arm will be provided a book (*Writing Down Bones* by Natalie Goldberg) about creative writing and will be asked to do activities for 1.5 hours every 2 weeks. After three months, control group participants can join creative writing workshops at their discretion for the remaining period for writing workshops. Both group members will receive follow up surveys twice a month for two months at the completion of the participant's two-month study period.

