9.4 Endpoints:**9.4.1 Primary endpoints:**

- Mood scores before (at baseline) and after intervention (after completion of entire sessions - this may vary as some patients may not be able to complete six sessions). A validated Emotional Thermometer Scales will be used to predict changes in parameters pre and post-intervention.
- Severity of depression and anxiety symptoms before and after intervention between two groups. Validated Depression and Anxiety questionnaires will be used to predict changes, the PHQ-9 and GAD-7 respectively.

9.4.2 Secondary endpoints:

[figure not shown]
- Mood and symptoms before and after at least 2 sessions of intervention.
- Self-reported somatic symptoms pre and post intervention in two groups. We will use the Somatic Symptom Scale – 8 (SSM-8) to quantify somatic symptom burden.
- Difference in scores and symptoms between various genders.
- Difference in scores and symptoms between patients living alone versus with family.
- Difference in scores and symptoms in different cancer types.
- Difference in scores and symptoms versus number of classes attended.
- Differences between individual mood scores for patients in the control group who later switch to intervention group and attend at least one session
- Mood and symptom scores up to 2 months after completion of the study.

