The control arm will receive a book (i.e., *Writing Down Bones* by Natalie Goldberg) on creative writing and asked to read and do writing activities for one and a half hours once every two weeks. At the completion of the two-month participation or completion of 4 sessions control patients will be given the opportunity to enroll in the creative writing workshops for the remainder of the study period of 6 months. We will collect scores from control arm through the same Emotion Thermometers Scale on a monthly basis. Pre-intervention scores will be obtained at the time of consent or one week prior to the planned start of session 1 for workshop (either in the clinic if possible or mail the score sheet to patients with an enclosed stamped envelope for return of the scales). Depending on participant preference, we can send them emails of the REDCAP surveys containing the same information at set intervals. A sample of the REDCAP surveys is included in supplementary materials. We will also send participants in the control arm a stamped return envelope on a monthly basis if not able to get score sheets in a clinic or over REDCAP, depending on patient convenience and preference. We will call the participants once every 3-4 weeks to check in on their progress. Please see a calendar at the end for details.

To assess for possible confounding results of patients participating in the concurrent exercise study, we will ask participants if they are also enrolled in the exercise study at enrollment and perform a subset analysis for patients who are in the exercise study. They will be randomized into either control or intervention group in the same manner as the other patients in the study. We will additionally include a section of the survey to ask about regular exercise (more than 30 minutes, three times a week) and do a subset analysis of these patients as well.

We will be collaborating with the Department of psychiatry at HMC - [name], [name], and [name]. Any subject who requests psychiatry follow up will be referred to [name]. If participants report the presence of suicidal ideation per question nine on the PHQ-9 [i.e., Thoughts that you would be better off dead or of hurting yourself in some way], they will be referred on an urgent basis to [name] or [name]. In the event [name] and/or [name] are unavailable for follow-up, If any active suicidal thoughts are reported, participants will be referred directly to Emergency Department at Hershey Medical Center.

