11.0 Statistical Plan

11.1 Statistical Analysis Plan

Participants' basic demographic and baseline clinical measurements will be summarized using descriptive statistics. Those summarizations will be based on all patients as well as on patients within each group. This study has several main groups of outcome variables, which reflect several different domains of patient's mental health. The first group is the emotion thermometer (which has five sub-scales), the second is the somatic symptom scale (SSS-8), the third is the Patient Health Questionnaire (PHQ-9), and the fourth is the Generalized Anxiety Disorder questionnaire (GAD-7), which measures participants' anxiety. All the above outcome variable groups are based on questionnaires using Likert-scale questions to take the measurements, and each group may involve multiple sub-dimensions. Both the intervention group and the control group have repeated measures of the outcomes as shown in Figure 1. Graphical methods (such as the line plot of mean/SD values vs. time) will first be used to illustrate the mean and standard deviation values of the mode, depression, and anxiety scores through the time for both groups. These methods will help us detect the patterns of how the scores change over time (within-group change) and how the scores differ between groups. We will further use the linear mixed-effect model for repeated measures to analyze the within-group and between-group differences. Every sub-dimension will be analyzed individually, but we will also analyze the composite score for the dimensions. For the patients in the control group this study involves two stages (week 1-12 and week 13-20), and at the end of the 12th week, they can join the intervention group. This setting will allow us to study the effect of the intervention on the control group alone. For this part of analyses, linear mixed-effect models will be set up with the stage serves as an indicator variable in the model. The comparison of outcome variables between certain time points will also be done using paired tests. We will further investigate the possible factors that might affect the change of outcome variables over time. The factors are gender, race, marital status, time from cancer diagnosis (first 3 months, 3-6 months, more than 6 months) and cancer stages. This part of analyses will mainly be focused on the intervention group and the above factors will be examined in the linear mixed-effect models. All analyses will be performed using statistical software SAS version 9.4 or higher (SAS Institute, Cary, NC, USA) and the statistical significance level to be used is 0.05.

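### The protocol contradicts itself on when controls may join the workshop, and section 11.1 neither ends the between-arm comparison at that time nor isolates the follow-up scores that run past it

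*Combined protocol and SAP*

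**What the plan says.** All references are to the current protocol version, which comes first in the combined document.

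**When controls may join.**
- Section 10.1: "At the completion of the two-month participation or completion of 4 sessions control patients will be given the opportunity to enroll" in the workshops for the rest of the six-month programme.
- Section 9.2: "After three months, control group participants can join creative writing workshops at their discretion for the remaining period for writing workshops".
- Section 10.6 has controls reading the book every other week for three months.
- Section 11.1, describing the comparator arm: "this study involves two stages (week 1-12 and week 13-20), and at the end of the 12th week, they can join the intervention group".

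**Follow-up.** Section 9.2 states: "Both group members will receive follow up surveys twice a month for two months", starting when the two-month study period ends. Section 10.1 starts the same surveys after a period of two to three months. Section 9.4.2 makes them a secondary endpoint: "Mood and symptom scores up to 2 months after completion of the study". Section 9.3 allows participation of 2 to 6 months, so workshop patients may also still be attending.

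**Analysis.** For the arms, 11.1 says: "We will further use the linear mixed-effect model for repeated measures to analyze the within-group and between-group differences". It names no last time-point. The switch is mentioned only for the analysis within the control group: "For this part of analyses, linear mixed-effect models will be set up with the stage serves as an indicator variable in the model".

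**Sample size.** Section 11.2 claims at least 80% power for 0.45 SD with 40 versus 20 patients, four time-points and a within-patient auto-correlation of 0.2. It does not say which four time-points.

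**The concern.** Three months and week 12 agree in substance; 10.1 is the outlier. The summary of changes attached to the protocol records that 10.1 was moved from three to two months and from 6 to 4 sessions, which suggests that the other sections were not brought into line.

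The mismatch has two consequences. First, a control who joins under 10.1 would be in the workshop for several weeks that 11.1's stage variable still codes as control. Second, the follow-up endpoint extends into a period when controls may be in the workshop and workshop patients may not have stopped. A shrinking difference there could be read as fading benefit when it is partly controls catching up, and a difference that persists could not be described as benefit outlasting the workshop.

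Because 11.1 sets no cut-off for the between-arm model, nothing in the text keeps such scores out of the randomised comparison.

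**Working it through.** **Step 1: timing.** Four sessions at one every two weeks take 4 × 2 = 8 weeks, so 10.1 opens the workshop from about week 9. Section 11.1's control stage runs to week 12, so about four weeks (9 to 12) can be miscoded. For follow-up, the stated joining times and survey start times combine as follows:

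| Joining allowed | Follow-up starts | Follow-up window | Part after joining is allowed |
|---|---|---|---|
| Month 2 (10.1) | Month 2 (9.2) | Months 2-4 | All |
| Month 2 (10.1) | Month 3 (10.1, upper end) | Months 3-5 | All |
| Month 3 (9.2, 11.1) | Month 3 (10.1, upper end) | Months 3-5 | All; 11.1's stage 2, weeks 13-20, is these eight weeks |
| Month 3 (9.2) | Month 2 (9.2) | Months 2-4 | Second month, about two of four surveys |

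No combination keeps follow-up clear of the joining time.

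**Step 2: reproduce the stated power.** Take the group effect averaged over four time-points, with AR(1) correlation 0.2, all four points carrying the effect, and two-sided 0.05 (11.1 does not state sidedness).
- Variance factor = [4 + 2(3×0.2 + 2×0.04 + 0.008)]/16 = 0.336.
- Standard error = √0.336 × √(1/20 + 1/40) = 0.159 SD.
- Power = Φ(0.45/0.159 − 1.96) = 80.9%.

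This matches the claim of at least 80%. Equal correlation between all visits would give 73.8%, so AR(1) is used below.

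**Step 3: a single follow-up point after joining is allowed.** Let p be the share of controls who join; the documents do not give it. Assume that a control gains the full effect at once and that the workshop arm keeps it. The expected difference is 0.45(1 − p):
- p = 25%: 0.34 SD
- p = 50%: 0.23 SD
- p = 75%: 0.11 SD

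**Step 4: the four-point model of 11.2.** If m of the four points fall after joining, the averaged effect is 0.45(1 − p×m/4).

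| Uptake | Effect, m = 2 | Power, m = 2 | Power, m = 1 |
|---|---|---|---|
| 0% | 0.45 SD | 80.9% | 80.9% |
| 25% | 0.39 SD | 69.9% | 75.7% |
| 50% | 0.34 SD | 56.6% | 69.9% |
| 75% | 0.28 SD | 42.5% | 63.4% |
| 100% | 0.225 SD | 29.4% | 56.6% |

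**Step 5: only points before joining is allowed**, 40 versus 20, same assumptions.
- Two points: variance factor (2 + 2×0.2)/4 = 0.60; power 56.4%; effect detectable with 80% power 0.59 SD.
- Three points: variance factor [3 + 2(2×0.2 + 0.04)]/9 = 0.431; power 70.6%; detectable effect 0.50 SD.

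**The case against.** **The model may stop in time.** A reader might infer that the between-arm model is planned to run past the switch. No passage says so. Section 11.1 refers to a schema for the repeated measures and 10.1 to a calendar, and neither is legible in the text available here. The four points of 11.2 could be baseline and months 1, 2 and 3, all at or before week 12, with little or no dilution if joining opens then. This stands: the dilution is permitted by the text, not prescribed. Under 10.1's joining time, however, the month-3 score could already be exposed.

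**Workshop against workshop.** A reader might describe the later scores this way. That needs every control to join. Joining is optional and late enrollees have little programme left. With even enrolment over 4.5 months and classes ending at month 6, at most (6−2)/4.5 = 89% of controls would have any programme left under the two-month rule, and (6−3)/4.5 = 67% under the three-month rule. On that assumption the 75% row is out of reach under the three-month rule. The fair description is the workshop arm against a mix of joined and unjoined controls.

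**A larger averaged dilution.** A reader might average the month 1 and 2 scores with four follow-up surveys. The documents describe no such model; 11.2 assumes four time-points.

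**The primary endpoint.** It compares baseline with completion of the sessions, which can precede joining, and the follow-up endpoint is secondary and claims no lasting superiority. Both points are correct. But completion is allowed to vary, and six fortnightly sessions take about 12 weeks, so primary scores are not guaranteed to come first.

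**Cutting off costs power.** This stands. With two points after joining, keeping them gives 69.9% power at 25% uptake, against 56.4% from two earlier points; the two approaches are level at about 50% uptake. The pooled estimate, however, no longer measures workshop against book, and its meaning depends on an uptake that nobody can know in advance.

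**Conclusion.** The concern holds in this form. The joining time is contradictory in the current text. Coded as 11.1 describes, a control who joins at about week 9 would be counted as unexposed until week 12. The follow-up endpoint reaches past the joining time on every reading, wholly so on all but one, and therefore cannot show lasting benefit over the book. Section 11.1 leaves open whether exposed scores enter the randomised comparison.

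The sizes in steps 3 and 4 are illustrations. They rest on assumed uptake, an immediate full effect on joining, and, for the power figures, AR(1) correlation of 0.2 with a two-sided test. A slower effect or lower uptake would shrink the dilution. The documents do not support saying that the primary result will be diluted, only that the plan does not prevent it. Nor do they support treating the remedy as nearly free: on 11.2's own assumptions, the uncontaminated comparison has well under 80% power at 60 patients.

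**What to change.** 1. Reconcile the joining time across 9.2, 10.1, 10.6 and 11.1. The timing is for the sponsor to choose. Align the start of follow-up in 9.2 and 10.1 at the same time.
2. Define the stage indicator in 11.1 by each control's actual joining date.
3. State in 11.1 that the primary between-arm contrasts for mood, PHQ-9 and GAD-7, and the SSS-8 contrast, use scores up to the time controls may first join, with all patients analysed by randomised arm. Check that the primary post-intervention score falls within that limit, including for patients who attend six sessions.
4. Report follow-up scores separately by randomised arm as immediate versus later offer, with the number of controls who joined and of workshop patients who continued. Make no claim from them of lasting benefit over the book.
5. Restate 11.2 for the time-points actually used, naming them and the correlation structure. On the assumptions above, power for 0.45 SD is about 56% with two points or 71% with three.

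The work is protocol and SAP wording plus one recalculation, and should be settled before uptake or outcomes are examined. The cost is a less favourable stated power and a more modest follow-up claim. Restoring 80% power for 0.45 SD would need 35 controls and 70 workshop patients with two points, or 26 and 52 with three; 11.2 says that workshop capacity largely set the present size.

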9.3 Study Duration

Estimated time to enroll all subjects = 3-5 months (Patients will start being enrolled after IRB approval and we will continue the enrollment up to 4-5 months from the time the 1st class starts for the intervention group)

Length of a participant's participation = 2 - 6 months; Follow up after participant's completion of classes = 2 months

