10.0 STUDY PROCEDURES

10.1 Methods: After enrollment as above, co-investigators of this study or the assigned coordinator will be doing the consent. Patient will be randomized to intervention and control arms in a 2:1 ratio. The intervention arm will receive a dedicated workshop for one and a half hours every 2 weeks. We aim to start a 6 month long program with weekly creative writings workshops, and patient enrollment in the study will continue through the 1st 4.5 months of the 6 month period so that the last enrolled patient could complete 2 classes per month for two months. Each patient will be asked to attend at least two classes per month for a total of two months. These workshops will be held at Hershey Medical Center (HMC). At the initiation of the study along with consent we will collect baseline scores in both groups for each parameter as below. Somatic Symptom Burden (SSM-8 - Figure 2 - reference section), depression symptoms using PHQ-9 (Figure 3 – reference section), and anxiety symptoms using GAD-7 (Figure 4 – reference section) will be collected monthly and following intervention completion.

We will collect mood scores pre and post each session. We will use Emotional Thermometer Scale (EMS) from [name] (Feb. 2010), diagram for scales is shown in figure 1. Please see supplementary index for a letter of permission to use from [name]. We will give the Thermometer scales and collect scores pre and post each session and also collect scores pre and post completion of entire course. Control group will do EMS on monthly basis along with other parameters. At the end of the study we will review all participants' medical charts to count view the number of emergency room visits and hospitalizations each participant experienced during the study period. These will be further broken down in categories based on cancer

Institutional Review Board

related vs non-cancer related visits. We will also review their most current cancer disease status after completion of the workshops and categorize whether their status is considered to be stable, progressing, or in remission. Both groups will also receive follow up mood and symptom surveys twice a month for up to 2 months after completion of the participant's two to three month study period.

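### Section 10.1 gives two baseline rules, one tied to workshop session 1, and neither requires baseline to precede randomisation, so a common pre-randomisation baseline is not guaranteed

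*Combined protocol and SAP*

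**What the plan says.** Section 10.1 sets the time of baseline twice. The first paragraph says "At the initiation of the study along with consent we will collect baseline scores in both groups for each parameter as below". The third paragraph, which is about the control arm, says "Pre-intervention scores will be obtained at the time of consent or one week prior to the planned start of session 1 for workshop" and lets this be done "either in the clinic if possible or mail the score sheet to patients with an enclosed stamped envelope for return of the scales".

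On randomisation, 10.1 says only "Patient will be randomized to intervention and control arms in a 2:1 ratio". This follows the sentence on consent, but no time is given relative to the baseline score or to telling the patient the arm. For controls, "We will collect scores from control arm through the same Emotion Thermometers Scale on a monthly basis". Section 9.3 says "Patients will start being enrolled after IRB approval and we will continue the enrollment up to 4-5 months from the time the 1st class starts".

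Section 9.4.1 makes before-after scores on the thermometers, PHQ-9 and GAD-7 the primary endpoints. The statistical plan (11.1) names a linear mixed model and paired tests. It does not say which record is baseline and states no baseline adjustment. The two baseline statements stand unchanged in all three protocol versions in the file.

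**The concern.** The two statements agree only if the second option is never used. That option is timed to a workshop session, and controls attend no workshop during the randomised period. If it is used after allocation is known, the baseline is no longer a pre-randomisation measurement, and it may sit at a different distance from consent in the two arms.

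This matters here for three reasons. Patients cannot be kept unaware of their arm. Every primary measure is self-reported. The recall windows are short: the past week for the thermometers and the last two weeks for PHQ-9 and GAD-7. A score taken some weeks after consent covers a different period and may reflect the patient's reaction to the allocation. In a before-after comparison, such a difference could not be told apart from an effect of the workshop, and adjusting for that score would not be adjusting for a pre-randomisation value.

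**Working it through.** **1. The rules side by side**

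| Question | 10.1, first paragraph | 10.1, third paragraph |
|---|---|---|
| When? | With consent | At consent, or one week before workshop session 1 |
| Who? | Both groups | Not stated |
| How? | Not stated | In clinic or by mail |
| Before randomisation? | Not stated | Not stated |
| Before the arm is known? | Not stated | Not stated |

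Section 8.1.1 has written consent taken at a clinic visit, so a mailed sheet can come back after that visit. The second option gives a date different from consent only when consent was more than a week before session 1. Whenever the option matters, there is therefore a gap in which randomisation and disclosure can fall. Section 9.3 opens enrolment after IRB approval and sets no limit on the wait until the first class.

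**2. The plan's own figure**

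Inputs from section 11.2: 40 and 20 patients, effect 0.45 SD, four time points, autocorrelation 0.2. Section 11.1 gives alpha 0.05; two-sided is assumed.

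- Variance of a four-measure mean under AR(1): V = [4 + 2(3×0.2 + 2×0.04 + 0.008)]/16 = 5.376/16 = 0.336.
- Standard error of the arm difference: √[0.336 × (1/40 + 1/20)] = √0.0252 = 0.159.
- Power (normal approximation): Φ(0.45/0.159 − 1.96) = 80.9%. With t on 58 df it is 79.6%.

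The stated 80% is reproduced under AR(1). Under compound symmetry, V = (1 + 3×0.2)/4 = 0.40 and power is 73.8%. Baseline timing is not an input, so reconciling the two rules changes neither sample size nor stated power.

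**3. What a shifted baseline would do**

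The documents give no figure for a shift. **Assumption:** the later option moves the workshop arm's baseline by s = 0.1 to 0.2 SD, with no true effect, one pre and one post score, and every workshop patient using it. Let ρ be the pre-post correlation.

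- Change score: bias s, variance 2(1 − ρ).
- ANCOVA: bias ρs, variance 1 − ρ².
- Standard error: √[variance × (1/40 + 1/20)].

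Example at ρ = 0.2, s = 0.2, change score: SE = √(1.6 × 0.075) = 0.346 and 0.2/0.346 = 0.577. Two-sided error = Φ(−1.96 + 0.577) + Φ(−1.96 − 0.577) = 0.083 + 0.006 = 8.9%.

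| ρ | s | Change score: bias (SD), type I error | ANCOVA: bias (SD), type I error |
|---|---|---|---|
| 0.2 | 0.1 | 0.10, 6.0% | 0.02, 5.1% |
| 0.2 | 0.2 | 0.20, 8.9% | 0.04, 5.3% |
| 0.5 | 0.1 | 0.10, 6.5% | 0.05, 5.5% |
| 0.5 | 0.2 | 0.20, 11.3% | 0.10, 7.1% |

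The bias scales with the share of workshop patients who use the later option. If half do, it halves.

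For an arm difference in the mean of four measures, the quantity behind the 0.45 SD, a shift in baseline alone contributes at most one quarter: 0.2/4 = 0.05 SD if baseline is one of the four, and nothing if it is not.

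**The case against.** The first paragraph of 10.1 already takes every scale with consent in both groups, and the third paragraph lists consent first. Site practice may have been sound throughout. Several stronger readings are tempting but go beyond the text.

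- **That baseline is taken after allocation is known.** No section gives the time of randomisation or disclosure. Session 1 could mean the programme's own start date, which exists whatever a patient's arm. Post-allocation timing is permitted and plausible, but not stated.
- **That only workshop patients use the later option.** The sentence has no such limit. It stands in the control-arm paragraph, shortly after controls are offered the workshops, and could refer to controls who join later.
- **That mood is bound to drift after a new diagnosis or progression.** Section 7.1 keeps that population, but 7.3 admits any patient with a cancer diagnosis, and 11.1 foresees patients more than six months from diagnosis.
- **That the gap is long.** Section 10.1 describes weekly workshops, so for patients enrolled once classes are running the two dates may nearly coincide. The exposed group is mainly those enrolled before the first class, and the length of their wait is not given.

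The schema in 9.5 and the calendar mentioned in 10.1 are not visible in the text and may settle the matter.

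These points limit how often the problem could arise and how large it could be. They do not remove it: two rules stand, they differ, and neither requires baseline to precede randomisation.

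**Conclusion.** The point holds as a conflict between two baseline rules in 10.1, one of which permits a baseline after allocation. The supportable statement is that a common pre-randomisation baseline is not guaranteed. The documents do not show that it is absent.

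Neither size nor direction is known. If anticipation of the workshop lowered that arm's later baseline, its apparent improvement would shrink; a higher baseline would inflate it. Disappointment among controls could act only if controls were also scored late, which the text neither says nor excludes.

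A reader might divide the assumed shift by the 0.45 SD target and report 0.1/0.45 to 0.2/0.45, or 22-44%, as the expected bias. That is not supported. The shift is assumed. The ratio applies only to an unadjusted change score or baseline-to-post contrast with every workshop patient using the later option. It also sets that contrast against an effect size that fits a mean over four time points. The statistical plan specifies neither a change score nor ANCOVA, so either figure in the table is conditional on a choice not yet made.

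This is a cheap improvement rather than a flaw that undermines the trial. Confidence is medium.

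**What to change.** - In the third paragraph of 10.1, delete the alternative of one week before session 1, so that both paragraphs give one rule.
- Require the thermometers, PHQ-9, GAD-7 and SSS-8 to be completed at the consent visit, in both arms, before the allocation is drawn or disclosed.
- Record the date of baseline and the date of randomisation.
- In 11.1, name that record as baseline in the mixed model.
- A later score before session 1 may be kept as a separate descriptive measure. It must not replace baseline.
- Check the schema and the calendar against the new rule.

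The cost is a slightly longer consent visit and the loss of the mail option for this one assessment. Consent is already taken at a clinic visit, so no extra visit is needed. Sample size and stated power do not change.
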